1 INTRODUCTION

This document presents a statistical analysis plan (SAP) for Ultragenyx Pharmaceutical, Inc. Protocol UX001-CL202 (*An Open-label Phase 2 Extension Study to Evaluate the Long Term Safety and Efficacy of Sialic Acid-Extended Release (SA-ER) Tablets and Sialic Acid-Immediate Release (SA-IR) Capsules in Patients with GNE Myopathy or Hereditary Inclusion Body Myopathy*).

Reference materials for this statistical plan include the Protocol UX001-CL202 (Original: 01 March 2013, Amendment #1: 02 October 2013), UX001-CL202 Case Report Forms (24 July 2013), feeder study Protocol UX001-CL201 and the SAP for UX001-CL201 (05 November 2013: Week 48 Analysis). Study UX001-CL202 is an Open-Label extension study and treatment is not blinded. Subjects completing 48-week in study UX001-CL201 are eligible to continue treatment under this open-label extension protocol testing an increased dose of SA. Additional GNE Myopathy subjects will be enrolled to assess the safety and efficacy of SA-ER/SA-IR in a treatment naïve population. Ultragenyx Pharmaceutical is conducting UX001-CL202 in two parts:

- Part I of the study will provide additional information on the long-term safety and efficacy of 6g/day SA ER;
- Part II of the study will assess the safety and efficacy of 1.5 g of SA-ER / 1.5 g of SA-IR treatment 4 times per day (12g/day SA-ER/SA-IR total dose) for 6 months. If reasonable efficacy and safety are demonstrated at the interim analysis at 6 months post initiation of part II, the subjects may continue therapy for up to 36 months.

The statistical plan described hereafter is an *a priori* plan. The SAP will be finalized and approved prior to completing inferential or descriptive analyses of data pertaining Ultragenyx Pharmaceutical, Inc. Protocol UX001-CL202. Statistical Analysis programming may occur as study data accumulate in order to have analysis programs ready at the time the study finishes. For the reasons stated herein the conduct of the study in the field is considered to be independent of any study outcome that might materialize upon enactment of the currently proposed statistical analysis plan.

2 STUDY OBJECTIVES

Study objectives defined in the protocol and amendment include safety, clinical endpoints, and exploratory objectives for both Part I and Part II of the study. Objectives are specified as follows from the protocol:

1.1. Safety Objectives

- Evaluate additional long-term safety of SA-ER treatment of GNE Myopathy subjects previously treated with SA-ER at dose of 6g/day (Part I).
- Evaluate the safety of 12g /day SA-ER/SA-IR (delivered by 1.5g of SA-ER tablets and 1.5g of SA IR capsules 4 times per day) in the treatment of GNE Myopathy subjects over a 6 month treatment period (Part II).

1.2. Clinical Objectives

- Evaluate the long-term effect of SA-ER/SA-IR treatment of GNE Myopathy subjects on muscle strength as measured by hand-held dynamometry (HHD).
- Evaluate the long-term effect of SA-ER/SA-IR treatment of GNE Myopathy subjects on mobility, strength, and function using a series of physical performance measures.
- Evaluate the effect of SA-ER/SA-IR treatment of GNE Myopathy subjects on functional disability using an interview-based questionnaire.

1.3. Exploratory Objectives

- Evaluate the effect of SA-ER treatment on serum biomarkers of sialylation in GNE Myopathy subjects (Part I).
- Determine whether 12g/day SA-ER/SA-IR administered 1.5g/1.5g four times per day is superior to prior treatment with SA-ER in GNE Myopathy subjects (Part II).

3 STUDY DESIGN

As background for the statistical methods presented below, this section provides an overview of the study design and plan of study execution. The protocol (plus protocol amendment) is the definitive reference for all matters discussed in what follows.

UX001-CL202 open-label extension study will assess the long term safety and efficacy of SA ER/SA-IR treatment over a period of approximately 36 months, or until marketing approval or program termination by Ultragenyx. In Part I of the study, approximately 46 subjects will be enrolled following successful completion of the UX001-CL201 study. The Baseline visit will be conducted in conjunction with the UX001-CL201 Week 48 study visit to avoid treatment disruption. Enrollment will take place after all UX001-CL201 Week 48 study assessments have been completed and the investigator has determined the subject meets all eligibility criteria. Data collected at the UX001-CL201 Week 48 visit will serve as the Baseline data for Part I of this protocol. Following the signing of informed consent at the Baseline visit, each subject will be dispensed a 6-week supply of study drug. Throughout the Part I Treatment Period of the study, all subjects will continue to take four 500 mg SA-ER tablets orally three times per day (TID), in the morning, early evening, and at bedtime (qHS), for a total dose of 6g/day. The Part I Termination Visit will also serve as the Baseline Visit for Part II of the study. However, for completion of the analysis with integrated information from UX001-CL201 subjects the baseline may be defined as the week 48 visit from UX001-CL201, or other such baselines from key time points in the UX001-CL201 study as may be defined for selected analyses to examine clinical endpoints.

Beginning with the Part II-Baseline Visit, all subjects currently enrolled in Part I will crossover to the SA-ER/SA-IR dosing regimen. An additional 10 treatment naive GNE Myopathy subjects will be enrolled into Part II of the study. The additional subjects will provide an assessment of SA-ER/SA-IR treatment in SA naïve subjects able to walk at least 200 meters (and < 80% predicted) in a screening 6 Minute Walk Test (6MWT). Throughout the 36-month Part II Treatment Period, all subjects will be administered 1.5g SA-ER and 1.5g SA-IR orally four times per day (QID), in the morning, afternoon, early evening, and qHS, for a total SA dose of 12g/day.

Evaluations of safety, changes in clinical endpoints such as muscle strength, mobility, and function, and changes in exploratory serum biomarkers will be performed according to the Schedule of Events specific to each phase of the study. A Part II Termination Visit will be conducted 4 weeks after subjects receive their last dose of study drug. Efficacy data analyses will be conducted at the end of the 36-month Part II Treatment Period, although additional analyses may be performed and documented at the discretion of Ultragenyx.

Safety will be monitored throughout the study based on physical examinations, clinical laboratory analyses, and reporting of adverse events (AEs) and SAEs. An independent Data Monitoring Committee (DMC) will review safety information periodically on an ad hoc basis as outlined in the DMC charter, which is maintained separately from this protocol.

A complete schedule of events specific for each part of the study is found in the protocol (Section 2, Tables 2.1 and 2.2) and repeated herein as [Table 1](#) and [Table 2](#).

Subjects enrolled in UX001-CL201 will roll over into UX001-CL202. In addition SA naïve treated subjects will be enrolled into Part II of UX001-CL202. [Figure 1](#) presents a summary of the time points and dosing expected for subjects participating in UX001-CL202, as well as outlining the key analysis time points: Additional analysis at 6 months after initiating Part II and the final analysis. (Note that the protocol refers to the 6 months analysis in Part II as an interim analysis. This analysis is being referred to as an additional analysis since this is an open label single arm study, and no formal adjustments for alpha spending will be employed in the study analyses).

Table 1 Schedule of Events (Part I)

ASSESSMENTS AND EVENTS	PART I TREATMENT PERIOD ^b (weeks)			PART I TERM VISIT ^c
	BASELINE ^a	6	12	
INFORMED CONSENT	X			
INTERVAL HISTORY ^d	X			X
VITAL SIGNS	X			X
HEIGHT AND WEIGHT	X			X
PHYSICAL EXAM ^e	X			X
NEUROLOGICAL EXAM	X			X
EFFICACY MEASURES				
HAND-HELD DYNAMOMETRY (HHD) ^f	X			X
6 MINUTE WALK TEST (6MWT) ^f	X			X
WALKING SPEED TEST ^f	X			X
WEIGHTED ARM LIFT TEST ^f	X			X
HIBM-FAS	X			X
CLINICAL LABORATORY TESTS				
CREATINE KINASE	X			X
SERUM PROTEIN MARKERS	X			X
FREE SERUM SA LEVELS ^g	X			X
FREE AND TOTAL URINE SA LEVELS ^g	X			X
CBC, CHEMISTRY, URINALYSIS	X			X
PREGNANCY TEST	X			X
ADVERSE EVENTS	X ^h	X	X	X
CONCOMITANT MEDICATIONS	X	X	X	X
TREATMENT DISPENSED	X	X	X	

^a Potential subjects for the Part I Treatment Period will be baselined at the UX001-CL201 Week 48 study visit. Study drug will be dispensed only after UX001-CL202 consent has been signed and all study procedures have been performed.

^b For Week 6 and 12 visits, the window is ± 0 days.

^c The Part I Termination Visit will also serve as the Part II Baseline Visit. For subjects who discontinue prior to completing the study, the Termination Visit will be considered an Early Termination Visit; every reasonable effort should be made to perform the Termination Visit procedures within four weeks of discontinuation.

^d Interval history will include any signs, symptoms, or events (e.g., falls) experienced by the subject since the prior study visit that are not related to study procedure(s) performed at prior study visits or study drug. Interval history may include exacerbation or improvement in existing medical conditions (including the clinical manifestations of GNE Myopathy) that might interfere with study participation, safety, and/or positively or negatively impact performance of functional assessments.

^e The physical examinations at all study visits will be complete.

^f Portions of the HHD, 6MWT, walking speed and weighted arm lift testing sessions may be videotaped to monitor administration technique and assess qualitative changes in function. Subject identity will be protected by blurring out the facial area in the video.

^g Trough levels of free SA in serum and free and total SA in urine.

[figure not shown]
^h Adverse Events will be collected after subject signs Informed Consent form.

Table 2 Schedule of Events (Part II)

ASSESSMENTS AND EVENTS	PART II TREATMENT PERIOD ^b (months)														TERM VISIT ^c
	SCREENING/ BASELINE ^a	1	3	6	9	12	15	18	21	24	27	30	33	36	
INFORMED CONSENT	X														
MEDICAL/INTERVAL HISTORY ^d	X	X		X		X		X		X		X		X	X
VITAL SIGNS	X	X		X		X		X		X		X		X	X
HEIGHT AND WEIGHT	X		X	X		X		X		X		X		X	X
PHYSICAL EXAM ^e	X			X				X						X	X
NEUROLOGICAL EXAM	X			X				X						X	
EFFICACY MEASURES															
HAND-HELD DYNAMOMETRY (HHD) ^f	X		X	X		X		X		X		X		X	X
6 MINUTE WALK TEST (6MWT) ^f	X		X	X		X		X		X		X		X	X
WALKING SPEED TEST ^f	X		X	X		X		X		X		X		X	X
WEIGHTED ARM LIFT TEST ^f	X		X	X		X		X		X		X		X	X
HIBM-FAS	X			X				X						X	X
CLINICAL LABORATORY TESTS															
CREATINE KINASE	X	X	X	X		X				X				X	X
FREE SERUM SA LEVELS ^g	X	X	X	X		X				X				X	X
CBC, CHEMISTRY	X	X	X	X		X				X				X	X
PREGNANCY TEST	X					X				X					X
ADVERSE EVENTS	X ^h	X	X	X	X	X	X	X	X	X	X	X	X	X	X
CONCOMITANT MEDICATIONS	X		X	X	X	X	X	X	X	X	X	X	X	X	X
DISPENSE STUDY DRUG ⁱ	X	X	X	X	X	X	X	X	X	X	X	X	X		
TREATMENT COMPLIANCE ^j	X	X	X	X	X	X	X	X	X	X	X	X	X	X	

- ^a The Part I Termination Visit will also serve as the Part II Baseline Visit for continuing subjects. SA naïve subjects will enter directly into Part II of the study (Part II Screening/Baseline Visit). SA-ER/SA-IR study drug will be dispensed only after UX001-CL202 (Part II) consent has been signed and all study procedures have been performed.
- ^b The Month 1 Visit window is ± 1 week. For all other Visits the window is ± 14 days.
- ^c The Part II Termination Visit occurs four weeks after subjects receive their last dose. For subjects who discontinue prior to completing the study, the Termination Visit will be considered an Early Termination Visit; every reasonable effort should be made to perform the Termination Visit procedures within four weeks of discontinuation.
- ^d For SA naïve subjects, medical history (including a detailed GNE Myopathy disease-specific history) will be reviewed at the Screening/Baseline visit. Interval history for all subjects will include any signs, symptoms, or events (e.g., falls) experienced by the subject since the prior study visit that are not related to study procedure(s) performed at prior study visits or study drug. Interval history may include exacerbation or improvement in existing medical conditions (including the clinical manifestations of GNE Myopathy) that might interfere with study participation, safety, and/or positively or negatively impact performance of functional assessments.
- ^e The physical examinations at all study visits will be complete.
- ^f Portions of the HHD, 6MWT, walking speed and weighted arm lift testing sessions may be videotaped to monitor administration technique and assess qualitative changes in function. Subject identity will be protected by blurring out the facial area in the video.
- ^g Trough levels of free SA in serum; record the time of last dose and sample collection.
- ^h Adverse Events will be collected after subject signs Informed Consent form.
- ⁱ A one month supply of study drug will be dispensed at scheduled treatment visits; additional study drug will be shipped directly to subjects between visits on a monthly basis.
- ^j Phone calls will be placed to each subject at least once between each study visit to assess treatment compliance with the dosing regimen. Additional telephone contacts with the subject may be placed as needed.

Figure 1 UX001-CL202 Study Periods and Analysis Map

** Participation in Part I varied by subject. The range of time for participation in Part I will be displayed by Subject in individual listings. Some Subjects who rolled over from UX001-CL201 went directly to Part II and the 12g/day SA-ER/SA-IR
 *** Additional snapshots of data may be taken earlier and later for analysis.

4 ANALYSIS POPULATIONS

The following analysis populations are defined for this study:

Safety Population (SAFETY): All subjects who provide informed consent and receive at least one dose of planned study medication in either Part I or Part II of the study and provide any post-treatment safety information. The safety population may be further sub-divided into Part I-Safety Population and Part II-Safety Population where appropriate for planned summaries. Subjects included in the safety population will be analyzed as treated. The Safety Population will be the source for all planned safety endpoints and analyses.

Intent-to-Treat Population (ITT): All subjects who are in the Safety Population and provide a least one (1) post-baseline clinical endpoint (efficacy) assessment over the course of the study will be included in the ITT Population. The ITT population may be further sub-divided into Part I-ITT Population and Part II-ITT Population where appropriate for planned analyses. Subjects included in the ITT population will be analyzed as treated. The ITT population will be the source for all planned clinical endpoint (efficacy) assessments and analyses.

Treatment Naïve Population (TNP): Subjects who are identified and enrolled into Part II of the study as treatment naïve subjects will be included in this analysis population and analyzed as a separate subgroup.

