7.3 Selection of Study Population

The study will be conducted in adult patients who have previously demonstrated mutations in the gene for the GNE/MNK enzyme leading to a diagnosis of GNE myopathy (variously termed HIBM, DMRV, or Nonaka disease). These patients are unable to synthesize endogenous SA, which leads to muscle weakness and atrophy. Consequently, this is the relevant population for testing SA replacement therapy to determine if exogenous SA leads to improved protein and lipid sialylation and stabilized or improved muscle structure and performance. The majority of the study population will consist of approximately 46 GNE Myopathy subjects who successfully completed UX001-CL201 and may or may not have

been previously exposed to SA-ER. Approximately 10 GNE Myopathy subjects who are SA and MaNAc-treatment naïve will be enrolled into Part II of the study.

The inclusion/exclusion criteria from the UX001-CL201 study inherently define the study population for subjects in Part I of the study, since successful completion of UX001-CL201 is requisite for enrollment in this study. The previous study was designed to allow for the enrollment of patients with a broad spectrum of physical disability, with at least 60% of enrolled subjects having residual lower extremity strength and function sufficient to walk ≥ 200 meters in the 6MWT. Enrolling patients across the spectrum of disease severity as subjects allowed the study to fully explore the safety and efficacy profile of SA-ER and inform the design of future studies. However, it should be noted that subjects unable to complete UX001-CL201 would not be eligible for this extension study, potentially introducing population bias toward subjects experiencing favorable safety and efficacy following up to 48 weeks treatment with SA-ER.

For the additional treatment naïve subjects enrolled into Part II of the study, the diagnosis and age range are the same as requirements for continuing subjects. This subgroup will be restricted to GNE Myopathy subjects with the ability to walk at least 200 meters during the 6MWT. Since the strongest clinical efficacy signal was observed in this subset of GNE Myopathy subjects participating in the UX001-CL201 study, this protocol was designed to enroll those subjects most likely to obtain clinical benefit from study treatment.

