7.6.1.1 Clinical Efficacy Analyses

All subjects with any post-dose data will be included in the intent-to-treat (ITT) efficacy analysis.

Efficacy will be evaluated by continued improvement in clinical assessments. Efficacy assessments may differ depending on the phase of the study (i.e., Part I, Part II, Part III, or

Part IV). For Part I efficacy evaluation, results from the last pre-treatment assessment from UX001-CL201 will be compared with the last post-treatment assessment for the Part I Treatment Period as listed in the Schedule of Events ([Table 2.1](#)), with efficacy conclusions based on change since SA-ER treatment initiation. An interim analysis will be conducted when a majority of subjects have completed the Month 6 Visit of the Part II Treatment Period. For Part II efficacy evaluation of the continuing subjects, change from baseline of Part II to Month 6 assessment at 12g/day SA-ER/SA-IR dose will be determined and compared with the improvement observed during the first 6 months of treatment with 6 g/day SA-ER dose, and to the rate of change observed with placebo or 3g treatment during the first 6 months of the study.

The changes from baseline of the treatment-naïve subjects will be evaluated over time. Potential comparisons of the changes from baseline to Month 6 will be performed for the 6MWT, UE, and LE between the naïve group versus the placebo and 6g/day treatment groups for the first 24 weeks of treatments in subjects able to walk more than 200m at baseline. In addition, changes in muscle strength over the entire treatment period of subjects who started with 6g/day and 3g/day will be evaluated and compared to the projected values of subjects who received placebo for the first 24 weeks of treatment in UX001-CL201.

A full accounting of the analyses for Parts III and IV of the study will be provided in the Statistical Analysis Plan.

For those clinical evaluations with repeated assessments (i.e., HHD, 6 MWT, walking speed and weighted arm lift tests) the analysis will be performed using a repeated measures analysis. An exchangeable variance-covariance structure will be used. The final treatment effect estimate based on this model will be the estimated treatment difference at Month 36. The purpose of including data from assessments prior to Month 36 is to increase the precision of the estimated variance, while using categorical effects of time-by-treatment to avoid modeling assumptions.

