5.1 Study Drug Dosing

Study Drug Dosing for the UX001-CL201 feeder study and for this study UX001-CL202 are mapped to present all possible treatment combinations that a subject may participate in within these two studies (Table 3).

Table 3 Study Drug Dosing Pathways: UX001-CL201 – UX001-CL202

Path	UX001-CL201		UX001-CL202	
	Weeks 0-24	Weeks 24-48	Part I	Part II
1	6g/day	6g/day	6g/day	12g/day
2	3g/day	3g/day	6g/day	12g/day
3	0g/day	6g/day	6g/day	12g/day
4	0g/day	3g/day	6g/day	12g/day
5	N/A	N/A	N/A	12g/day

The 0/6 and 0/3 treatment groups (pathways 3 and 4) may be combined during weeks 0-24 for UX001-CL201 subjects to form a placebo group for comparisons with pathway 5.

The 0/6 and 6/6 treatment groups (pathways 1 and 3) and 0/3 and 3/3 treatment groups (pathways 2 and 4) may be combined to form 3g and 6g treatment groups for comparison with the 12g/day SA-ER/SA-IR dosing.

A total of 5 separate treatment pathways are identified for evaluation. Subjects enrolled in UX001-CL202 who are members of the TNP will have no treatment pathway from the UX001-CL201 study. Subjects who roll over from UX001-CL201 into Part I of this study will continue on a dose of 6g/day SA-ER. These data will be used primarily for additional safety data. All subjects participating in Part II of this study will receive 12g/day SA-ER/SA-IR. The focus of the safety analyses for the primary objective will be on safety at the 6g/day SA-ER and safety at the 12g/day SA-ER/SA-IR doses.

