6 STATISTICAL METHODOLOGY

6.1 Sample Size

Approximately 46 subjects may be enrolled in Part I of this open-label extension study. Sample size is limited to the number of subjects enrolled in the Phase 2 safety and efficacy study, UX001-CL201, who achieve at least 80% treatment compliance and study visit completion. As Part I of the study is intended to evaluate the long-term safety of 6g/day SA-ER in subjects with GNE Myopathy and ascertain the long-term effect of SA-ER treatment on muscle strength, mobility, and functional disability, the sample size is deemed reasonable to satisfy Part I study objectives.

An additional 10 subjects will be enrolled into Part II of the study. This subset of treatment naïve GNE Myopathy subjects will provide additional safety and efficacy information following treatment with SA-ER/SA-IR. Note that more than 10 planned subjects may be enrolled in this subset of treatment naïve GNE Myopathy subjects, as new subjects are identified at the study centers. These additional subjects will only add additional information and informative value to this treatment naïve GNE Myopathy population. No modifications of updates to the SAP are needed for additional subjects in this group.

The study design is open-label with all subjects receiving the same treatment. Therefore, the study is not powered to assess statistically significant comparisons. Instead, the sample size is intended to provide the maximum amount of long-term safety and efficacy data for the investigational product.

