6.7 Statistical Analysis: Clinical Efficacy

6.7.1 Planned Comparisons for Clinical Efficacy Parameters

The planned comparisons for UX001-CL202 are based on change from baseline assessments, where different baselines are utilized to evaluate treatment across a subject's treatment in

both UX001-CL201 and UX001-CL202. [Table 8](#) presents the planned comparisons for study data obtained in UX001-CL202 compared with study data from UX001-CL201 for roll-over subjects, as well as the treatment naïve subjects in UX001-CL202.

Clinical efficacy data collected in Part I of UX001-CL202 (all roll-over subjects dosed with 6g/day SA-ER) will not be included in planned comparisons for the clinical efficacy analysis.

Additional comparisons not specified in this statistical analysis plan may be completed as prospective analyses are completed to better understand study results. These additional comparisons will be clearly identified in final reporting.

Table 8 Planned Comparisons

Planned Comparison	Description
Primary Analysis #1: Week 24 12g/day SA/ER/SA-IR vs. Week 0	All subjects who roll-over from UX001CL201 will have their week 0 assigned as baseline (Part I termination visit of the 202 study) and the change from this score will be compared to the week 24 12g/day SA-ER/SA-IR treatment to assess the impact of the 12g/day SA-ER/SA-IR dose.
Primary Analysis #2: Week 24 12g/day SA/ER/SA-IR vs. Week 48 UX001-CL201 for 6/6+0/6 SA-ER	All subjects who roll-over from UX001CL201 will have their week 48 assigned as baseline and the change from this score will be compared to the week 24 12g/day SA-ER/SA-IR treatment to assess the impact of the 12g/day SA-ER/SA-IR dose across the combined 6/6+0/6 dose (UX001-CL201 subjects treated with 0/6 or 6/6 SA-ER will be combined for comparison from dosing pathways 1 and 3 from Table 3). A second comparison will be with a 6 minute walk test at Screening of ≥ 200 m (6MWT ≥ 200 m)
Primary Analysis #3: Week 24 12g/day SA/ER/SA-IR vs. Week 48 UX001-CL201 for 3/3+0/3	All subjects who roll-over from UX001CL201 will have their week 48 assigned as baseline and

Planned Comparison	Description

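### Read literally, the SAP limits the CL201 placebo comparator for the treatment-naïve group to placebo subjects who finished 48 weeks and rolled over, a limit that Table 8 and the protocol do not state

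*SAP*

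**What the plan says.** SAP section 4 gives a single source for efficacy: "The ITT population will be the source for all planned clinical endpoint (efficacy) assessments and analyses". It defines that population as "All subjects who are in the Safety Population and provide a least one (1) post-baseline clinical endpoint (efficacy) assessment". The Safety Population in turn requires subjects to "receive at least one dose of planned study medication in either Part I or Part II of the study", meaning CL202.

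SAP section 5.1 says that the 0/6 and 0/3 groups, labelled pathways 3 and 4, "may be combined during weeks 0-24 for UX001-CL201 subjects to form a placebo group for comparisons with pathway 5". In Table 3 both pathways run on through CL202 Parts I and II. Pathway 5 is the naïve group.

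The text introducing Table 8 in SAP section 6.7.1 describes CL202 data "compared with study data from UX001-CL201 for roll-over subjects", and the same sentence then adds the treatment-naïve subjects. The Table 8 row for the Treatment Naïve Secondary Analysis names the CL201 placebo-treated subjects and restricts them only by a 6MWT of at least 200 m.

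Protocol section 7.6.1.1 describes potential comparisons "between the naïve group versus the placebo and 6g/day treatment groups for the first 24 weeks of treatments", in subjects able to walk more than 200 m at baseline. It states no rollover condition.

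On rollover subjects generally, protocol section 7.3 warns that "subjects unable to complete UX001-CL201 would not be eligible for this extension study, potentially introducing population bias toward subjects experiencing favorable safety and efficacy".

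**The concern.** The comparison covers the first 24 weeks on each side. Under the section 4 rule, a placebo subject's Week 0-24 data count only if that subject went on to complete Weeks 24-48, on active drug, and then entered CL202. A placebo subject with complete data to Week 24 who stopped at Week 30 would be removed because of something that happened after the outcome was measured. A naïve subject needs only one dose and one post-baseline efficacy assessment.

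Selecting one side on later events can bias the difference. If the placebo subjects who left had declined more by Week 24, the retained placebo mean is too favourable and an effect of 12 g/day is understated. If they had done better, the effect is overstated. Existing data would also be dropped from a small comparator.

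This is the only row of SAP Table 8 that sets 12 g/day against placebo, and section 8.1 repeats it for each efficacy endpoint. If the comparator is not stated outright, two programmers could build different ones.

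**Working it through.** **Step 1: trace who can be in the comparator under section 4.**

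- All planned efficacy analyses use ITT (SAP section 4).
- ITT lies inside the Safety Population (SAP section 4).
- The Safety Population requires a dose in CL202 Part I or II (SAP section 4).
- A former CL201 subject enters CL202 only after successfully completing CL201 (protocol section 7.3.1), which lasts 48 weeks (SAP section 1).

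So a CL201 placebo subject is in the source population only after completing 48 weeks and being dosed in CL202. Building the group from pathways 3 and 4 (SAP section 5.1) points the same way.

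**Step 2: set this against the text that defines the contrast.**

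- In Table 8, Primary Analyses #1 to #3 and the Secondary Analysis each begin by limiting the row to subjects who rolled over. The naïve-versus-placebo row does not, and restricts only on 6MWT.
- Protocol section 7.6.1.1 names the placebo group over its first 24 weeks, with no rollover condition.
- SAP section 6.5.1 says the SAP analyses are consistent with the protocol.
- SAP section 6.5.11 plans pooled data sets built from the final CL201 analysis data, where appropriate, without saying which subjects.

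Nothing in these passages exempts the comparator from the section 4 rule, and nothing in section 4 acknowledges the wider wording of Table 8. The texts give two different comparators.

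**Step 3: how large could it be?** The plan gives no figure to reproduce: no effect size, SD or power is stated. The documents also omit the CL201 placebo arm size, the number of placebo walkers and the number who did not roll over. What follows rests on assumptions.

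*Shift in the placebo mean.* If k of m eligible placebo subjects are excluded and their mean change differs from that of the retained subjects by d SD, the retained mean differs from the full mean by (k/m) × d.

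*Assumed m.* Three equal arms of 46: 46/3 = 15.3. With 60% walking at least 200 m (the CL201 enrolment minimum in protocol section 7.3): 15.3 × 0.60 = 9.2, taken as 9.

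| Excluded | d = 0.5 | d = 1.0 | d = 1.5 |
|---|---|---|---|
| 0 of 9 | 0 | 0 | 0 |
| 1 of 9 | 0.06 SD | 0.11 SD | 0.17 SD |
| 2 of 9 | 0.11 SD | 0.22 SD | 0.33 SD |

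*Scale.* With 10 naïve and 9 placebo subjects, a two-sided 5% two-sample t-test (noncentral t) has 80% power for a difference of 1.37 SD. Holding that difference fixed:

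| Excluded | Power, no bias | Power, excluded subjects 1 SD worse |
|---|---|---|
| 1 of 9 | 77.1% | 70.0% |
| 2 of 9 | 73.6% | 58.4% |

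Part of each fall is lost sample size and part is the shift. If the excluded subjects had done better than the rest, the shift would inflate the apparent effect.

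**The case against.** The strongest reply is that the row defining this contrast already means all placebo subjects. It drops the rollover wording that the rollover rows carry. Section 4 defines populations for CL202 and need not govern data from a completed period of another trial. Section 5.1 is permissive and speaks of CL201 subjects. The rollover phrase in section 6.7.1 may describe only the rollover rows, since the naïve subjects are listed separately in the same sentence. SAP section 3 makes the protocol the definitive reference. All of this stands as evidence of intent, so it cannot be said that the SAP certainly excludes these subjects. It does not remove the conflict, because section 4 covers all planned efficacy analyses and makes no exception.

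Four stronger readings are tempting, and the documents do not support them:

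- **That comparators must also pass a compliance filter.** SAP section 6.1 refers to subjects "who achieve at least 80% treatment compliance and study visit completion", but this is a sample-size sentence. The parallel protocol text (section 7.6.4) and the inclusion criteria contain no such condition.
- **That this is the only 12 g/day versus placebo contrast anywhere.** It is the only one in SAP Table 8. Protocol section 7.6.1.1 also compares the rollover subjects' 12 g/day change with the placebo rate of change.
- **That one or two of nine were in fact lost.** Protocol section 7.6.4 ties the 46 to CL201 enrolment, and section 7.3 describes about 46 as CL201 completers. Taken together, few or none may have been lost, and 9 may be nearer the retained number than the full one.
- **That the power figures forecast this trial.** The planned model is a covariate-adjusted GEE, the 1.37 SD effect is chosen only to give 80% power, and both documents say the study is not powered for comparisons.

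**Conclusion.** The point holds as a conflict over the comparator population. Taken literally, SAP sections 4 and 5.1 limit the Week 0-24 placebo comparator to subjects selected on events after that window, with no matching condition on the naïve group. Table 8 and protocol section 7.6.1.1 state no such limit. Protocol section 7.3 recognises completer selection for rollovers, and neither document carries that through to this contrast.

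The size and direction of any bias cannot be determined. It is zero if every eligible placebo subject rolled over. The shifts of 0.06 to 0.33 SD, and the power figures, depend on assumed equal arms, a 60% walking share, one or two exclusions and an assumed difference for those excluded.

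The contrast is a secondary, open-label comparison of about 10 subjects with non-concurrent controls, and no sample size depends on it. The reason to act is that the population is ambiguous and one reading is open to avoidable bias.

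**What to change.** In SAP sections 4 and 6.7.1, for the Treatment Naïve Secondary Analysis:

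1. Define the comparator as all CL201 subjects randomised to placebo with Screening 6MWT of at least 200 m and at least one post-baseline assessment in Weeks 0-24. Take them from the CL201 analysis data sets whether or not they entered CL202.
2. State that the CL202 ITT rule and Table 3 pathways 3 and 4 do not restrict this comparator.
3. Report how many of these subjects did not roll over.
4. Keep the rollover-only version as a sensitivity analysis.

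This takes a few sentences. Section 6.5.11 already plans to use the final CL201 data sets, so no new data, visits or patients are needed. The downside is one extra run. If no eligible placebo subject was lost, the two versions coincide and the report can say so.
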